**Development of Culturally Sensitive and
Patient-Centered Feedback for Alzheimer's
Dementia Risk Disclosure**

NCT04309500

IRB Approval Date: January 26, 2022

Uploaded: 09/29/2022

Intervention:	
Stage I: Observational study (needs assessment); no intervention
 
Stage II: Behavioral Intervention: personalized Dementia-Alzheimer's type risk disclosure feedback

Key Inclusion Criteria:	
Stage I: Human volunteers who are consensus diagnosed as cognitively healthy or with Mild Cognitive Impairment (MCI) with ability to consent; ≥ 65 years of age; first-language English; identified co-participant who is cognitively healthy, has known the participant for ≥ 5 years, and has at least weekly phone/in-person contact with the participant
 
Stage II: Same as Phase I, plus participants must have a negative baseline screen for clinically significant depression or anxiety on standardized measures and already be followed by a medical provider.

Key Exclusion Criteria:	Stage I & II: Significant uncorrected sensory impairment, severe neurologic or psychiatric diagnosis; consensus diagnosis of dementia
Study Type:	Interventional, single-group design
Primary purpose:	
Stage I: Complete assessment of needs, preferences, and rationale regarding DAT risk disclosure in participants and their family members of diverse racial-ethnic backgrounds
 
Stage II: Develop and pilot personalized DAT risk disclosure protocols with participants and family members of diverse racial-ethnic backgrounds; investigate initial outcomes including comprehension/recall of results, satisfaction, and psychological reactions immediately following risk disclosure and at 1- and 6-weeks following risk disclosure

Phase:	I/II (Stage II Behavioral Intervention Study)
Date of First Enrollment:	
Stage I: 10/22/19
 
Stage II: 10/1/20 (anticipated)

Target Sample Size:	
Stage I: up to 120 (60 participant/co-participant dyads)
 
Stage II: 20 (10 participant/co-participant dyads)

Recruitment Status:	
Stage I: Currently recruiting
 
Stage II: Currently recruiting

Primary Outcomes:	
Stage I:
 
 (a) Interest in different levels of risk disclosure feedback (b) Preferences for different levels of risk disclosure feedback (c) Perceived personal threat of DAT (d) Perceived benefits of/rationale for risk disclosure (e) Perceived barriers to risk disclosure (f) Importance of risk disclosure feedback elements 
Stage II:
 
 (a) Comprehension/recall of personal risk information (b) Psychological distress (mood, anxiety, and event-specific distress) (c) Satisfaction with feedback process (exploratory)

SECTION 1: Roles & Responsibilities - Contributorship

[name]. (ARF) – Principal Investigator

Affiliations: University of Michigan, Department of Psychiatry

Contact: [contact]

Roles & Responsibilities:

Design conception and initiation
Preparation of protocol and revisions
Managing correspondence with clinical trials office
Publication of study reports
Preparation of manuscripts
Recruitment and screening of patients
Data collection
Data entry, verification
Statistical Analyses
Regulatory and compliance management/adverse event reporting

[name]., ABPP-CN (BMH) – Co-Investigator

Affiliations: VA Ann Arbor Healthcare Systems, Mental Health Service

University of Michigan, Department of Psychiatry

Contact: [contact]

Roles & Responsibilities:

Design conception and initiation
Mentorship

J. [name]. (JSR) – Co-Investigator

Affiliations: University of Michigan, School of Public Health

Contact: [contact]

Roles & Responsibilities:

Design conception and initiation
Mentorship

[name], B.S. (ML) – Research Associate

Affiliations: University of Michigan, Department of Psychiatry

Contact: [contact]

Roles & Responsibilities:

Preparation of protocol and revisions
Managing correspondence with clinical trials office
Preparation of study reports
Preparation of manuscripts
Recruitment and screening of patients
Data collection
Data entry, verification
Statistical Analyses
Regulatory and compliance management/adverse event reporting

ARF conceived of the study, developed and refined the study protocol, and is responsible for study implementation, including data collection, entry, and management under the mentorship and direction of *BMH* and *JSR* and with assistance from *ML*. *BMH* will assist with development and psychometric evaluation of measures used in the study, as well as clinical characterization of participants. *JSR* will assist with development and adaptation of measures from the REVEAL study to the SHARE(D) Project, as well as integration of needs assessment information into Stage II feedback protocols. *ARF* will complete statistical analysis, prepare manuscripts and presentations, with editing input from *BMH* and *JSR*. *ARF* will manage the clinical trial registry, preparation of institutional review board materials, administrative duties, and auditing/reporting requirements for the various agencies associated with the study.

Roles & Responsibilities – Sponsor(s)/Funder(s)

This project was supported via an R03 award granted to ARF from the NIH/NIA. The funding source had no role in the design, execution, analyses, or interpretation of the study, nor will it have a role in the decision to submit results.

SECTION 2: INTRODUCTION

SECTION 2.1: Background & Rationale

As of 2018, an estimated 5.5 million Americans have late-onset dementia due to Alzheimer's disease (DAT), and another 11.6 million have Mild Cognitive Impairment (MCI)¹, with proportionately higher prevalence per capita in ethnic minorities¹⁻². Improved knowledge of health and lifestyle contributions to DAT trajectories have made early detection and disclosure of DAT risk a priority for researchers and clinicians alike. In fact, early disclosure of elevated risk would save an estimated \$172,000 per patient³ and \$8 trillion nationally¹ in healthcare costs via health behavior change and long-term planning. Given that African Americans incur significantly higher dementia-related costs than any other demographic⁴, early DAT risk feedback could be proportionately more beneficial for this population, yet occurs less frequently in these communities⁵.

Literature suggests that between 50-90% of individuals are interested in receiving dementia risk feedback^{6,7}. In this context, there is a gap between the rapid advancement of techniques to quantify DAT risk⁸ and development of empirically-supported methods to communicate this information to patients. A survey of the current AD risk disclosure literature revealed three critical knowledge gaps that build on our experience and inform the aims of this project.

Need 1: Feedback regarding personal DAT risk is undermined by a lack of knowledge about the type(s) of information patients and their families want to receive - and why. With the acceptance of the Amyloid-Tau-Neurodegeneration (A/T/N) model of Alzheimer's disease (AD)⁹, there is increased focus on how biomarkers may increase risk for the phenotypic presentation of AD (i.e., DAT). Advanced methods of detecting AD-related changes in genes, brain structure and function, biomarker burden, and cognition have expanded our ability to predict an individual's risk for future decline^{8,10-11}. However, little is known about whether patients would prefer to receive this more advanced (but experimental) information, as opposed to clinically-available (i.e., familiar) information. Most published studies in this area disclose DAT risk based on data gathered in clinical visits, such as family and personal medical history, subjective symptoms, and cognitive screening or neuropsychological testing. These studies have found that the vast majority of participants are interested in this feedback for long-term planning purposes^{6,7}.

Among biological risk factors, apolipoprotein epsilon-4 (APOε4) allelic status^{8,12} and positron emission tomography (PET) based amyloid burden^{5,7,13-15} have received the most attention in the risk disclosure literature, albeit in cognitively healthy individuals primarily. These studies indicate that patients' desire for risk information is high but varies as a function of how much they know about DAT and AD biomarkers¹⁶⁻¹⁸. There exists great variability in reasons for requesting risk disclosure, ranging from basic curiosity to family planning^{6-7,16-17}. Additionally, post-disclosure, even cognitively healthy participants have difficulty understanding feedback language (e.g., interpreting a "positive" biomarker as a "good" outcome¹²). Comparing across these single-source risk disclosure studies may be misleading, however, as none have directly compared what type of feedback patients would want to receive given a menu of all possible risk factors. In the absence of such a study, we suggest that clinical, genetic, and biomarker feedback is likely to be processed differently by patients. Genotype and family history are static, representing non-modifiable susceptibility. Cognitive test scores represent concrete measurements of changes that may already be apparent to patients and caregivers. In contrast, biomarkers are unfamiliar measurements of the individual's underlying level of AD pathology and are probabilistic rather than deterministic for a diagnosis of DAT. In light of these differences, the need to compare patient preferences for different sources of risk feedback is critical.

Advancement 1: This study will conduct a needs assessment of diverse patients' and informants' risk disclosure preferences. Aim 1 will evaluate patient and informant preferences for different sources of information used to determine DAT risk (see Table 1). Our inclusion of both patients and informants is especially relevant given our¹⁹ and others'²⁰⁻²² work showing discrepancies in self- and informant-rated cognitive deficits. The proposed project will include a sample that is racially diverse (see Advancement 2), unlike prior studies that have focused primarily on White older adults. Furthermore, the sample will include both cognitively symptomatic (MCI) and intact older adults, rather than focusing on healthy populations alone. Results will describe the unique disclosure needs of African-American and White participants and their families.

Need 2: To date, most feedback protocols have taken a one-size fits all approach to DAT risk disclosure, ignoring known strengths and challenges faced by racial-ethnic minority populations. Not only must we understand the type and amount of information patients want during DAT risk disclosure (Advancement 1), but also how and why racial groups differ in their preferences. Discussions of racial disparities in DAT prevalence tend to focus only on differences in biological risk factors (e.g., genetics, cardiovascular health), ignoring the complex epigenetic interplay between biology and environment. Sociocultural and socioeconomic differences (i.e., early educational differences, bias in cognitive testing, delayed/inadequate health care services, cultural stigma surrounding diagnosis) account for significant variance in DAT diagnosis and treatment in minority populations, even after controlling for biological risk factors². One such sociocultural difference may be the extent to which African American individuals request, have access to, and utilize DAT risk disclosure in early stages of the AD course. The sparse literature on the topic indicates that African Americans may be less interested in DAT risk feedback²³, yet reasons why are unknown. Greater understanding of African-American perspectives on risk disclosure will facilitate better communication and treatment, which in turn may alleviate the larger health disparities faced by this population.

Advancement 2: The proposed needs assessment will investigate recipient-specific factors that influence DAT risk disclosure preferences in African-American and White participants and informants.

The few studies examining risk disclosure preferences in non-White populations^{16-17,23-24} suggest that African-American individuals are more likely than White counterparts to decline feedback about DAT risk. More nuanced preferences about amount, type, and reasons for feedback in African-American versus White participants remain unknown. Similarly, the *reasons* behind this discrepancy have never been directly studied. For White participants, personal characteristics such as general or dementia-specific anxiety^{6,18,24,25} and knowledge of AD biomarkers, symptoms, course, treatments^{24,25} influence preferences for type and amount of feedback. These same factors – perceived vulnerability to DAT and DAT knowledge – appear to be lower in African-American individuals²⁴ but it is unclear if these group differences drive the decreased desire for DAT risk disclosure. We will directly evaluate patient characteristics that contribute to feedback preferences in a sample of African-American and White participants using an application of the Health Belief Model (HBM)²⁶. More specifically, we will study how perceived vulnerability to DAT, perceived seriousness of DAT, perceived benefits of DAT risk disclosure, and perceived barriers to effectively using DAT risk information shape feedback preferences.

Need 3: Our ability to effectively communicate DAT risk to participants and informants is limited by a lack of empirically-supported methods that integrate multiple risk factors. Existing studies have often taken a “siloed” approach that fails to integrate the multiple sources of DAT risk. Several studies have analyzed pre-disclosure desire to learn about a specific risk factor^{6,7,16-18}, or reactions to real¹² or simulated¹² single-source risk disclosure. Many provide guidelines for single risk-factor feedback^{7,12,27-30}, though these suggestions are abstract and drawn from investigations of mostly White, highly educated participants. To date, no study has developed a feedback protocol that integrates multiple DAT risk factors (clinical, genetic, neuroimaging, and biomarker) and can be adapted to meet the needs of racially diverse patients.

Advancement 3: This study will produce preliminary person-centered, culturally-informed protocols for communicating multi-factorial DAT risk, with specific adaptations in style or content based on patient-specific factors. Aim 2 will integrate the results of the existing literature and the Aim 1 needs assessment into practical feedback protocols, with initial piloting. Our approach not only attempts to replicate prior findings on psychological reactions to risk disclosure, but also extends the literature (a) by assessing protocol effectiveness in terms of patient and informant comprehension, recall, and satisfaction (exploratory), and (b) by comparing African American and White older adults’ reactions to feedback. The project will result in a

Table 1. Sources of DAT Risk Information Used in Feedback

Level 1: No information provided (no feedback)

Level 2: Standard Clinical Information

- Reported Family History
- Subjective Cognitive Complaints (Self + Informant)
- Neurological Examination
- Neuropsychological Evaluation

Level 3: Neurodegeneration

- Structural MRI (3D T1/T2)
- FLAIR

Level 4: Genetic Information

- APO-E ε4 allelic status

Level 5: A/T Biomarker Information

- Amyloid PET (PiB)
- Tau PET (¹⁸F Flortaucipir)

preliminary series of standardized protocols with specified adaptations (e.g., additional psychoeducation modules or language changes for impaired individuals) that can be integrated based on individual needs.

SECTION 2.2: Objectives & Hypotheses of the pilot study

Objective 1: to investigate the preferences and needs of racially diverse participants, and their respective informants, in regards to receiving feedback about their risk for DAT. We will leverage the robust Michigan Alzheimer's Disease Research Center (MADRC) infrastructure to recruit older adults who are asymptomatic (i.e., cognitively intact) or in the early stage of disease progression (Mild Cognitive Impairment [MCI]), half of whom will be African American. Utilizing mixed qualitative and quantitative methods in the Stage I Needs Assessment, we will systematically evaluate three questions:

1.1 Do African-American and White participants or co-participants differ in their interest in receiving certain types of DAT risk information? The study will evaluate group differences in participant and co-participant interest in and actual preference for feedback at five levels: (1) no information about AD risk, or risk information based on (2) standard clinical measures, (3) genetic information, (4) quantitative structural neuroimaging, (5) amyloid and tau PET. Exploratory analyses will assess whether group differences also exist based on clinical research diagnosis (normal vs. MCI), and whether participants and their co-participants agree.

1.2 Do African-American and White participants or co-participants differ in their perspectives on/rationale for certain types of DAT risk feedback? This study will assess whether African-American and White participants and co-participants identify different primary reasons for risk disclosure (i.e., basic curiosity, emotional reason, financial planning, medical planning, legal planning, social/family planning, or other). Exploratory analyses will assess whether group differences also exist based on clinical research diagnosis (normal vs. MCI), and whether participants and their co-participants agree.

1.3 Which characteristics predict risk disclosure interest in African-American vs. White participants and co-participants? This study will evaluate whether African-American and White participants and co-participants differ in their perceived threat of DAT, perceived benefits of risk disclosure, and perceived barriers to using risk information. We will also determine whether different factors (including personal demographic characteristics and the aforementioned perceived threat, benefits, and barriers) predict risk disclosure interest in different groups. Exploratory analyses will assess whether group differences also exist based on clinical research diagnosis (normal vs. MCI), and whether participants and their co-participants agree.

1.4 Which components of feedback do African-American and White participants or co-participants see as most important? This study will evaluate whether African-American and White participants and co-participants differ in their perspectives on the relative importance of different component of risk disclosure (e.g., educational materials, visual aids, follow-up coordination with providers). Exploratory analyses will assess whether group differences also exist based on clinical research diagnosis (normal vs. MCI), and whether participants and their co-participants agree.

Objective 2: to develop person-centered, culturally-informed protocols for disclosure of different combinations of Alzheimer's dementia risk factors. Building on the results of Objective 1, we will produce protocols for communication of DAT risk, with attention to specific adaptations in style or content based on the above noted individual factors. In particular, protocols will specify (a) effective methods of communicating risk conferred by each data source, (b) information designed for patients versus informants, (c) psychoeducation needs, and (d) resource/support needs. Through piloting in Stage II, we will evaluate three outcomes in both participants (those receiving the feedback) and co-participants:

2.1 Comprehension and recall of personal risk disclosure information

2.2 Psychological reactions to personal risk disclosure information

2.3 Satisfaction with the feedback process (exploratory)

SECTION 2.3: Trial Design

The Stage I Needs Assessment is an observational study with no intervention or randomization. Stage II will involve a clinical trial, with the risk disclosure feedback serving as the behavioral intervention. The study will use a single-group design. All 10 participant-co-participant dyads (5 Non-Hispanic African-American, 5 Non-Hispanic White) will receive feedback about the participant's DAT risk. Outcomes will be measured immediately following feedback and at 1- and 6-weeks following risk disclosure. For more information regarding design, see *Methods* section.

SECTION 3: METHODS

SECTION 3.1 Participants: Inclusion & Exclusion Criteria

3.1.1 Stage I

Participants (those identified as the person who would hypothetically receive DAT risk feedback) will be recruited from the Michigan Alzheimer's Disease Research Center's University of Michigan Memory and Aging Project (UM-MAP), Testing High Definition transcranial Direct Current Stimulation (HD-tDCS) as Treatment of Mild Cognitive Impairment Project (STIM), or Dementia in African American Population Phenotyping from Potential Elevated Risk (DAPPER) project.

Participants will include up to 60 older adults, age 65+ years who have completed an initial evaluation as part of the University of Michigan Memory and Aging Project (UM-MAP), the Testing High Definition transcranial Direct Current Stimulation (HD-tDCS) as Treatment of Mild Cognitive Impairment (STIM) project, or as part of the Dementia in African American Population Phenotyping from Potential Elevated Risk (DAPPER) project. Consistent with the diversity-related goals of this study, 25 of these participants will be self-reported Non-Hispanic African-American, and 25 will be self-reported Non-Hispanic White. As exploratory analyses will look at the role of cognitive impairment, approximately 50% of the sample will be consensus-diagnosed as either cognitive healthy or with Mild Cognitive Impairment (MCI; single- or –multiple domain, amnesic or non-amnesic forms) through their participation in UM-MAP, STIM, or DAPPER. Exclusion criteria include current or historical neurologic disorder (e.g., Alzheimer's dementia or other neurodegenerative dementia, Parkinson's disease, seizure disorder, tumor, multiple sclerosis) or neurologic injury (e.g., significant stroke or moderate-severe head injury, defined by loss of consciousness > 5 minutes, presence of significant post-traumatic amnesia, or the need for extended hospitalization or intervention). Participants with motor symptoms indicative of a neurodegenerative etiology other than Alzheimer's disease will also be excluded. Participants with severe mental illness (i.e., bipolar disorder, thought disorder, psychosis) or anyone deemed to meet criteria for current substance use disorder will be ineligible for participation in this study.

Co-Participants (those who are currently serving as a caregiver to the participant, or would hypothetically serve in this role should the need arise) include up to 60 adults, age 18+ years. Co-participants must be cognitively healthy, as defined by consensus diagnosis if they are also enrolled in UM-MAP, STIM, or DAPPER, by neuropsychological evaluation within 12 months of study participation, or by cognitive screening (MoCA) prior to study enrollment. As it is critical that co-participants can reliably and validly report on their perspectives or thoughts about their respective participants, co-participants must have known the participant for ≥5 years and have at least weekly phone or in-person contact with the participant.

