3.4.2.1 Stage I

Primary Outcome 1.1 (Differences in risk disclosure interest and preferences): To analyze the dichotomous yes/no interest outcomes, chi-squared analyses will be used to compare the proportion of African-American and White participants who endorse interest in receiving feedback at each level, for caregivers and patients separately. Given that there are five levels of risk disclosure feedback, five comparisons will be conducted; to account for the relatively small sample size, a conservative Bonferroni correction for multiple comparisons will be implemented ($\alpha = .05/5 = .01$). To analyze the Likert-style interest outcomes, either independent samples *t*-tests or Mann Whitney U tests will be used to compare mean interest level in African-American and White participants for each of the five risk disclosure levels, again using a Bonferroni correction. Further exploratory correlation analyses will determine agreement between caregiver and informant interest in African-American and White subgroups, separately.

Primary Outcome 1.2 (Differences in risk disclosure rationale): This study will assess whether African-American and White participants and co-participants identify different primary reasons for risk disclosure (i.e., basic curiosity, emotional reason, financial planning, medical planning, legal planning, social/family planning, or other), a Fisher's Exact test will be used, comparing frequency of reason endorsement. These analyses will be conducted for patients and informants separately; however, we will also explore agreement among dyad members.

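### Stage I sets the diagnosis target for the whole sample and compares races without regard to diagnosis, so an uneven MCI split by race could distort the participant race contrasts by an unknown amount

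*Combined protocol and SAP*

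**What the plan says.** Section 3.1.1 fixes race: "25 of these participants will be self-reported Non-Hispanic African-American, and 25 will be self-reported Non-Hispanic White". The ceiling is higher ("Participants will include up to 60 older adults, age 65+ years"), and Section 2.2 repeats the even race split ("half of whom will be African American"). The diagnosis target is separate: "approximately 50% of the sample will be consensus-diagnosed as either cognitive healthy or with Mild Cognitive Impairment". Taken literally, that sentence would place half the sample in either category. The sensible reading is about half healthy and half MCI. Nothing in the document crosses this target with race.

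Participants come from three parent studies. The title of UM-MAP refers to neither race nor MCI. The other two are "Dementia in African American Population Phenotyping from Potential Elevated Risk (DAPPER) project" and "Testing High Definition transcranial Direct Current Stimulation (HD-tDCS) as Treatment of Mild Cognitive Impairment Project (STIM". No number or cap per source is given, and neither study's eligibility rules appear.

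For outcome 1.1, Section 3.4.2.1 says that "chi-squared analyses will be used to compare the proportion of African-American and White participants who endorse interest in receiving feedback at each level", with t or Mann-Whitney tests for the ratings. Outcome 1.2 uses Fisher's exact test, and outcome 1.4 uses t or Mann-Whitney tests. None of these has a stratum or covariate. The participant factors listed for the 1.3 mixed model are demographics, anxiety, depression and DAT knowledge. Diagnosis appears in Section 2.2 as a separate exploratory comparison of normal with MCI, for which Section 3.4.2.1 gives no method.

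**The concern.** The race contrast and the diagnosis contrast are planned one at a time. A two-group race comparison also picks up any third factor that differs between the groups and affects the outcome. Diagnosis could be such a factor: its total is targeted, but its split by race is left to recruitment. Comparing normal with MCI separately may show that diagnosis matters, but it does not remove diagnosis from the race comparison.

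The race contrasts are the central Stage I result. Section 2.1 wants to know how and why the groups differ, and Section 2.2 builds the Stage II protocols on the answers. A diagnosis effect could be read as a difference between racial groups, or a real difference could be hidden.

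**Working it through.** **The plan's own figure.** The per-test level for outcome 1.1 is .05/5 = .01, which reproduces. No Stage I power or sample-size calculation is stated, so there is none to check.

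**Inputs.** From Section 3.1.1: 25 per race and about 25 MCI in all. From Section 3.4.2.1: chi-squared by race at .01 (taken here as two-sided, without continuity correction). Assumed, because the document gives neither: the MCI split by race, and interest by diagnosis.

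**How uneven can the split be?** With 25 per race and 25 MCI in total, anything from 13/12 to 25/0 satisfies the plan. If diagnosis were unrelated to race, the number of MCI cases m in one race would follow

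P(m) = C(25, m) × C(25, 25 − m) / C(50, 25).

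The gap between races is |2m − 25|. A gap of 5 or more (m ≤ 10 or m ≥ 15) has probability 25.8%, 7 or more 8.9%, and 9 or more 2.3%. A gap of 15 (20/5) or more has probability about 0.00005.

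**False difference.** With no race effect within diagnosis,

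false gap = (MCI share in race A − MCI share in race B) × (interest if normal − interest if MCI).

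For 20/5 at 90% and 60%: (20/25 − 5/25) × (0.90 − 0.60) = 0.60 × 0.30 = 18 points.

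**Rejection by the planned test.** The number interested in each race is the sum of two binomials, one for MCI and one for normal. Summing over all pairs of counts for which chi-squared exceeds its .01 critical value gives:

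| Assumed interest, normal / MCI | 15/10 | 18/8 | 20/5 |
|---|---|---|---|
| 90% / 60% | 6 points, 1.4% | 12 points, 4.3% | 18 points, 12.1% |
| 80% / 60% | 4 points, 1.2% | 8 points, 2.3% | 12 points, 4.7% |
| 90% / 80% | 2 points, 1.1% | 4 points, 1.5% | 6 points, 2.3% |
| 80% / 80% | 0 points, 1.1% | 0 points, 1.1% | 0 points, 1.1% |

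(The 18/8 split has 26 MCI cases, which still counts as about half.) The last row shows no inflation when diagnosis does not matter. At 30 per race the pattern is similar: 24/6 at 80% and 60% gives 12 points and 5.9%.

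**Ratings.** In a simulation with 40,000 runs per setting, a 20/5 split and a normal-to-MCI difference of 0.5, 0.8 or 1.0 SD, the t-test rejects at .01 in 5.4%, 14.2% and 23.5%.

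**Masking.** Assume a true 30-point race gap within each diagnosis (60% normal and 30% MCI in one race, 90% and 60% in the other), with more MCI in the higher-interest group. Power at .01 is 31% at 13/12, 9% at 18/8 and 4% at 20/5.

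**After stratifying.** In the 90% / 60% scenarios, a Cochran-Mantel-Haenszel test stratified by diagnosis rejects in 0.8% to 0.9% of simulated trials at all three splits. For ratings, a linear model with race and diagnosis rejects in 1.0% to 1.1% even at 20/5. The cost is precision. With half the sample MCI, the race-diagnosis correlation r equals the difference in MCI shares, and the variance of the race effect rises by 1/(1 − r²). At 17/8 this is 1/(1 − 0.36²) = 1.15, and at 20/5 it is 1/(1 − 0.60²) = 1.56.

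**The case against.** A reader might infer that the parent studies build a race-diagnosis imbalance into the sample, so that the race differences will be artefacts of recruitment. The document does not support that. The link to race or to MCI rests on two study titles. An imbalance would need DAPPER to be skewed on diagnosis or STIM on race, and neither is stated. The imbalance may be nil. Chance alone mostly gives small gaps, and at 15/10 the rejection rate is at most 1.4% in the table above.

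A reader might also infer that the MCI share within each race is purely a product of the quota. That goes too far, because only the overall total is targeted. Section 2.1 reports higher prevalence in ethnic minorities and ties diagnosis to sociocultural factors, so part of an uneven split could be real. Stage I is an observational needs assessment (Section 2.3), and an unadjusted contrast is a legitimate description of the people enrolled. Stratifying answers a different question.

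Three further limits stand. Co-participants must be cognitively healthy (Section 3.1.1), so their contrasts are affected only through the diagnosis of the person they answer about. Stage II disclosure is personalised on diagnosis, risk level and the indicators requested (Section 3.3.2), so a misread Stage I contrast would not directly decide what a person is told. And the exploratory diagnosis comparison means that a marked diagnosis effect would probably be noticed.

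These points limit the size and reach of the concern without removing it. The unadjusted contrast cannot show how much of a difference is diagnosis mix, and the plan's interest in why groups differ makes that question relevant.

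**Conclusion.** The gap in the plan is real, and its effect is conditional. Diagnosis is neither balanced within race nor accounted for in the race analyses, and the separate exploratory comparison does not correct them. A distorted participant race contrast needs both an uneven MCI split by race and an effect of diagnosis on the outcome, and the document quantifies neither. Over the assumed rates and splits shown, false rejection at .01 for the yes/no outcome ranges from no inflation to 12.1%. The upper end needs a 20/5 split, which chance would almost never produce, together with a 30-point difference in interest by diagnosis. It marks the edge of a range and is not a forecast. A stratified result beside the unadjusted one is justified because it uses data already held and leaves the descriptive contrast in place.

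**What to change.** 1. Report participant counts by race and diagnosis.
2. Keep each unadjusted participant race contrast as the descriptive result. Beside it, report a version stratified by diagnosis: Cochran-Mantel-Haenszel for the yes/no items of 1.1, van Elteren for the ratings in 1.1 and 1.4, and a stratified exact test for 1.2.
3. Add participant diagnosis to the 1.3 model.
4. For any enrolment still open, aim for about half MCI within each race, and reword the target sentence in Section 3.1.1 to say so. Stage I has enrolled since 10/22/19, so this step may come too late. The first three do not depend on it.

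The cost is one extra result for each participant contrast (every feedback level and component, so more than a few lines), some loss of precision if the split is uneven (variance up by 1.15 at 17/8 and 1.56 at 20/5), and possibly slower final enrolment.
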